3.2 Nivolumab Dose and Schedule

Nivolumab will be administered at a dose of 480mg IV every 28 days. Treatment with nivolumab will begin after an initial 7-day treatment period with abemaciclib monotherapy (see Figure 1: Treatment Schema). No dose modifications of nivolumab are permitted. Subjects who experience toxicity related to nivolumab will be managed in accordance with guidelines in the management algorithms provided in the nivolumab package label, with modifications relevant to the treatment population

Table 4: Dose Modifications and Delays For Nivolumab Toxicity

Adverse Reaction	Severity	Dose Modificaiton
Colitis	Grade 2 diarrhea or colitis	Withhold dose
	Grade 3 diarrhea or colitis	Withhold dose
	Grade 4 diarrhea or colitis	Permanently discontinue
Pneumonitis	Grade 2 pneumonitis	Withhold dose
	Grade 3 pneumonitis	Permanently discontinue
Hepatitis	
• If AST/ALT is within normal limits at baseline and increases to more than 3 and up to 5 times the ULN• If AST/ALT is more than 1 and up to 3 times ULN at baseline and increases to more than 5 and up to 20 times the ULN	Withhold dose
	If AST or ALT increases to more than 20 times the ULN or total bilirubin increases to more than 3 times the ULN	Permanently discontinue
Hypophysitis	Grade 2 or 3 hypophysitis	Withhold dose
	Grade 4 hypophysitis	Permanently discontinue
Adrenal Insufficiency	Grade 2	Withhold dose
	Grade 3 or 4	Permanently discontinue
Type 1 Diabetes Mellitus	Grade 3 hyperglycemia	Withhold dose

CONFIDENTIAL

This material is the property of the University of Pennsylvania.

	Grade 4 hyperglycemia	Permanently discontinue
Nephritis	Serum creatinine more than 1.5 and up to 6 times the ULN	Withhold dose
	Serum creatinine more than 6 times the ULN	Permanently discontinue
Skin	Grade 3 rash or suspected Stevens-Johnson syndrome (SJS) or toxic epidermal necrolysis (TEN)	Withhold dose
	Grade 4 rash or confirmed SJS or TEN	Permanently discontinue
Encephalitis	New-onset moderate or severe neurologic signs or symptoms	Withhold dose
	Immune-mediated encephalitis	Permanently discontinue
Other	Other Grade 3 Adverse Reaction (except for amylase or lipase elevations in absence of clinical pancreatitis)	
 Withhold dose for first occurrence Permanently discontinue for recurrence of same Grade 3 adverse event
	Life-threatening or Grade 4 adverse reaction	Permanently discontinue
	Grade 3 myocarditis	Permanently discontinue
	Requirement for 10mg per day or greater of prednisone or equivalent for more than 12 weeks	Permanently discontinue
	Persistent grade 2 or 3 adverse reactions lasting 12 weeks or longer	Permanently discontinue

These dose adjustments are for AEs deemed related to nivolumab using CTCAE v. 5.0. If in the opinion of the treating Investigator, a toxicity is thought to be unrelated to nivolumab, no dose delay for nivolumab is necessary. If treatment is withheld per the above table, it should be held until the toxicity has returned to Grade ≤ 1 .

Subjects with drug-related endocrinopathies controlled with hormone replacement such as insulin or adrenal replacement-dose steroids may resume treatment when toxicity has improved to Grade ≤ 1 . Dose interruption is not required for hyper- or hypothyroidism but supportive care (e.g. thyroid replacement) should be started per institutional standards.

Corticosteroids are frequently indicated for Grade 3 or greater toxicities, and are necessary at times for lower grade toxicities. Guidance for their use and dosing is available in nivolumab package label. For any toxicity of nivolumab (regardless of grade) that, despite optimal supportive care, is felt by the treating Investigator to present a risk to safety of the study subject, additional treatment delay or treatment discontinuation is permitted at the discretion of the treating Investigator.

3.4 Study Endpoints

3.4.1 Primary Study Endpoint

The primary study endpoint is overall response rate by investigator review using RECIST v. 1.1

3.4.2 Secondary Study Endpoints

1. Toxicity rates is an ordinal measure, graded using CTCAE v. 5.0, or dichotomized (binary)
2. Overall response rate using iRECIST criteria (binary)
3. Progression-free survival (time to event)
4. Duration of response (time to event)
5. Overall survival (time to event)

4 Study Population

4.1 Inclusion Criteria

1. Subjects must have hepatocellular carcinoma (HCC) that is inoperable (where surgery is not indicated due to disease extent, co-morbidities, or other technical reasons)
2. Histologic confirmation of HCC is not required for screening but is required prior to initiation of study treatment. Subjects with hepatocholangiocarcinoma or cholangiocarcinoma are not eligible.
3. Tumor must be positive for retinoblastoma (RB) expression by immunohistochemistry
4. Age \geq 18 years and ability to understand and the willingness to sign a written informed consent document.
5. ECOG performance status of 0 or 1
6. Childs-Pugh score of ≤ 7
7. Life expectancy of at least 12 weeks
8. Must be able to swallow tablets
9. Must be willing to comply with protocol procedures (including completion of diaries and outcome measures)
10. Local or loco-regional therapy to the liver (i.e. surgery, radiation therapy, hepatic arterial embolization, chemoembolization, radiofrequency ablation, percutaneous ethanol injection, or cryoablation) must have been completed ≥ 4 weeks prior to enrollment
11. Must be willing to undergo a pretreatment and on-treatment biopsy and have a tumor site that is accessible for core needle biopsy
12. Measurable or evaluable disease as defined by RECIST v. 1.1
13. Women of childbearing potential must have a negative serum pregnancy test performed within 7 days of the first dose of abemaciclib (see Appendix A for definition of childbearing potential). Female subjects of childbearing potential must use an approved contraceptive method (detailed in Appendix A) for the duration of the study and an additional 3 weeks after the final dose of abemaciclib.
14. Subjects with hepatitis B must have an HBV viral load < 100 IU/mL by PCR during screening
15. Must have adequate organ and hematopoietic function as defined below:

Table 5: Baseline Laboratory Parameters

Laboratory Test	Required Value
Absolute neutrophil count (ANC)	$\geq 1.5 \times 10^9/L$
Platelet count	$\geq 75,000 \times 10^9/L$
Hemoglobin	$\geq 8.0 \times 10^9/L$

CONFIDENTIAL

This material is the property of the University of Pennsylvania.

Alanine aminotransferase (ALT)	$\leq 3 \times \text{ULN}$
Aspartate aminotransferase (AST)	$\leq 3 \times \text{ULN}$
Serum creatinine	$\leq 1.5 \times \text{ULN}$
OR creatinine clearance (CrCl)	OR $\text{CrCl} \geq 50 \text{mL/min}$ by Cockcroft-Gault Formula
Total bilirubin	$\leq 2.0 \times \text{ULN}$
Serum albumin	$\geq 2.8 \text{ g/dL}$
INR	< 1.5 (FFP permitted if elevated)

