4.4 Total Number of Subjects and Sites

Twenty-seven evaluable subjects will be enrolled. Subjects may be enrolled at the University of Pennsylvania or at the Penn Presbyterian Medical Center.

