7.10.2 Definition of Evaluable

Evaluable for toxicity: All patients will be evaluable for toxicity from the time of their first treatment with abemaciclib.

Evaluable for efficacy endpoints, including overall response: Only those patients who have measurable disease present at baseline, have received at least one cycle of therapy (including at least 50% of scheduled abemaciclib doses and at least 1 dose of nivolumab), and have had their disease re-evaluated by appropriate imaging after at least 4 and no more than 12 weeks from cycle 1 day 1 will be considered evaluable for efficacy endpoints including overall response. These patients will have their response classified according to the definitions stated below.

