7.10.5 Response Criteria

7.10.5.1 Evaluation of Target Lesions (RECIST 1.1)

Complete Response (CR): Disappearance of all target lesions. Any pathological lymph nodes (whether target or non-target) must have reduction in short axis to <10 mm.

Partial Response (PR): At least a 30% decrease in the sum of the diameters of target lesions, taking as reference the baseline sum diameters

Progressive Disease (PD): At least a 20% increase in the sum of the diameters of target lesions, taking as reference the smallest sum on study (this includes the baseline sum if that is the smallest on study). In addition to the relative increase of 20%, the sum must also demonstrate an absolute increase of at least 5 mm. (Note: the appearance of one or more new lesions is also considered progressions).

Stable Disease (SD): Neither sufficient shrinkage to qualify for PR nor sufficient increase to qualify for PD, taking as reference the smallest sum diameters while on study.

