8.3 Sample Size and Power Determination

Overall response rate to PD-1 therapy in HCC has varied in published studies from 15-20%. By combining available data from these studies, an overall response rate of 18% is estimated for PD-1 monotherapy. Doubling of this response rate, from 18% (H0) to at least 36% (H1) would be highly promising and worthy of additional study. With 27 subjects, a one-sided binomial test with alpha = 0.10 will have 81% power to detect an improvement in ORR from 18% (H0) to 36% (H1). For proportions, a sample of n=27 will provide 90% confidence intervals that are a maximum of 0.34 in width. For additional time to event variables, 27 subjects (21 events by 24 months) yields 90% confidence intervals for median survival that are approximately half of mean survival in width (assuming exponential survival).

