8.4.2 Efficacy Analysis

To be eligible for efficacy endpoints (PFS, ORR, DOR, OS), subjects must have completed at least one cycle of therapy, and have had their disease re-evaluated by appropriate cross-sectional imaging (CT or MRI) at least 4 weeks and no more than 12 weeks after their baseline imaging. Subjects who do not meet criteria for the efficacy analysis will be replaced.

CONFIDENTIAL

This material is the property of the University of Pennsylvania.

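### Inclusion criterion 12 admits subjects without measurable disease, whom section 7.10.2 bars from the response analysis and section 8.4.2 does not

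*Combined protocol and SAP*

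**What the plan says.** - **Entry.** Section 4.1, item 12, requires "Measurable or evaluable disease as defined by RECIST v. 1.1". The two terms are alternatives. Section 7.10.3 sorts disease into measurable and non-measurable and does not define *evaluable* disease.
- **Evaluability, section 7.10.2.** Efficacy endpoints, including overall response, are limited as follows: "Only those patients who have measurable disease present at baseline". Treatment and re-imaging conditions are added.
- **Efficacy analysis, section 8.4.2.** "To be eligible for efficacy endpoints (PFS, ORR, DOR, OS), subjects must have completed at least one cycle of therapy", plus re-imaging within a window. Measurable disease is not mentioned. The section adds: "Subjects who do not meet criteria for the efficacy analysis will be replaced".
- **Response, sections 7.10.5.1 and 7.10.5.4.** The response rate is the proportion with a complete or partial response as best response. Partial response is "At least a 30% decrease in the sum of the diameters of target lesions, taking as reference the baseline sum diameters".
- **Target lesions.** The target-lesion paragraph of 7.10.3 allows evaluable as well as measurable lesions to be chosen. The RECIST 1.1 versus iRECIST table in 7.10.5.3 treats everything beyond the measurable target lesions as non-target.
- **Size.** Section 4.4: "Twenty-seven evaluable subjects will be enrolled". Section 8.3: a "one-sided binomial test with alpha = 0.10 will have 81% power" to detect a rise in response rate from 18% to 36%.

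**The concern.** Entry is wider than the population in which the primary endpoint is meant to be scored, and the two sections that define that population disagree on the point where entry is wider. A subject whose only disease is, for example, bone lesions or nodes of 10 to 14 mm in short axis meets item 12, fails 7.10.2 and can pass 8.4.2. No section says which rule prevails.

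Two things are at stake. If such subjects are excluded, people receive two drugs and, by default, a pretreatment and an on-treatment biopsy without adding to the primary endpoint. If they are kept, the denominator holds subjects with little prospect of a scored response. In an open-label trial with investigator-read responses, it is better to settle the denominator before any response is known.

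**Working it through.** **Inputs.** n = 27 evaluable (4.4); one-sided exact binomial test at 0.10, null rate 0.18, alternative 0.36 (8.3, 8.4). The documents give no number of subjects without measurable disease. The values m = 1, 2, 3 and the shares of 5% to 20% below are assumptions.

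**Step 1: reproduce the plan's power.** Take the smallest r with P(X ≥ r | 27, 0.18) ≤ 0.10.
- r = 7 gives 0.200, which is too large.
- r = 8 gives 0.0977, so success is 8 or more responses.
- Power = P(X ≥ 8 | 27, 0.36) = 0.812, which matches the stated 81%.

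**Step 2: 8.4.2 applied alone.** Let m of the 27 lack measurable disease, stay in the denominator and be certain non-responders. The threshold stays at 8, but only 27 − m subjects can respond.
- Power = P(X ≥ 8 | 27 − m, 0.36).
- Type I error = P(X ≥ 8 | 27 − m, 0.18).
- Expected response rate under the alternative = 0.36 × (27 − m)/27.

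| m | Power | Type I error | Expected rate |
|---|---|---|---|
| 0 | 81.2% | 0.098 | 36.0% |
| 1 | 77.4% | 0.081 | 34.7% |
| 2 | 72.9% | 0.066 | 33.3% |
| 3 | 68.0% | 0.053 | 32.0% |

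Each such subject costs about 4 to 5 points of power.

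**Step 3: exclusion under 7.10.2, replacement under 8.4.2.** All 27 analysed subjects have measurable disease, so power stays at 81.2%. Each excluded subject adds one to the number treated. With an assumed share f, the number to treat is 27/(1 − f), rounded up:
- 5%: 27/0.95 = 28.4, so 29
- 10%: 27/0.90 = 30
- 15%: 27/0.85 = 31.8, so 32
- 20%: 27/0.80 = 33.75, so 34

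**Step 4: is zero response the right assumption?** The texts point in different directions.
- Under the 7.10.5.3 table, a subject without measurable lesions has no target lesions and so no diameter sum that can fall by 30%. Section 7.10.5.2, headed for non-target lesions, repeats the target-lesion criteria and so offers no separate route to response.
- Under the target-lesion paragraph of 7.10.3, an evaluable lesion may be selected and measured, and could in principle score a partial response.

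Zero response is therefore the worst case, and the losses in step 2 are upper limits for the given m.

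**The case against.** The strongest reply is that the sample size is stated as 27 evaluable subjects, and 7.10.2 is the section that defines the term. On that reading all 27 have measurable disease and the planned power is untouched; 8.4.2 is merely silent. This stands, and it makes the power loss conditional. It does not remove the extra exposure, and it does not explain why 8.4.2 restates the efficacy criteria without the condition.

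Second, such subjects are probably few. Item 11 requires a tumor site accessible to core needle biopsy, histology and RB status must be known before treatment, and uncontrolled ascites is excluded. A subject with only an effusion is unlikely to qualify, and one with only sub-centimetre lesions might often not. Exclusions 18 and 23 also let the investigator refuse subjects whose endpoints cannot be evaluated. All of this stands as to frequency, but none of it requires measurable disease, and exclusions 18 and 23 are discretionary.

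Third, excluded subjects still contribute safety data, and section 7.11.2 lets biopsies be omitted in a subject's interest. Both points are correct; biopsy is the default, not a certainty.

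A reader might infer that the stated 81% power is wrong, or that the mismatch could produce a false positive result. The documents support neither. The 81% reproduces exactly, and keeping certain non-responders in the denominator lowers type I error.

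**Conclusion.** The mismatch is real and should be fixed, as a cheap improvement. Item 12 admits subjects whom 7.10.2 excludes from the response analysis and 8.4.2 does not. Replacement comes from 8.4.2; 7.10.2 only excludes.

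The cost is either one extra treated subject for each one admitted, with power unchanged, or, with 8.4.2 alone and no possibility of response, a fall in power to the values for m = 1 to 3 in the table. The second figure rests on an assumed number of subjects and a worst-case response rate. Its direction is conservative: the trial becomes more likely to miss a real effect, not to claim a false one.

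A reader might also infer that these subjects cannot respond at all. The text does not establish that, because the target-lesion paragraph of 7.10.3 and the table in 7.10.5.3 conflict. That conflict is a further reason to reconcile the wording.

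**What to change.** Make four wording changes in one amendment:
1. **Section 4.1, item 12:** require at least one measurable lesion by RECIST v1.1 on the baseline CT or MRI, and remove the evaluable-disease alternative.
2. **Section 8.4.2:** add measurable disease at baseline as a condition, to match 7.10.2.
3. **Section 7.10.3, target lesions:** restrict target lesions to measurable ones, deleting the reference to evaluable lesions.
4. **Section 7.10.3, size thresholds:** align them with the table in 7.10.5.3. The text has more than 10 mm on CT and more than 15 mm for nodes; the table has at least 10 mm and at least 15 mm. Without this, a borderline lesion could qualify a subject under one section and not the other.

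No procedure is added: baseline imaging is already required within 21 days of cycle 1 day 1 (Table 6, footnote 11), so measurability can be known before dosing. The planned n, threshold and power are unchanged. The downside is that a few candidates with only non-measurable disease are screened out; under 7.10.2 they could not have contributed to the primary endpoint.

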4.2 Exclusion Criteria

1. Any history of a serious medical or psychiatric condition that would prevent the subject from signing the informed consent form
2. Pregnant or breastfeeding
3. Use of any chemotherapy within 3 weeks prior to the first study treatment date
4. Use of any experimental therapy within 4 weeks or 5 half-lives, whichever is longer, prior to the first study treatment date
5. Use of radiation within 2 weeks prior to the first study treatment date (4 weeks if radiation to liver as per section 4.1)
6. Prior treatment with a CDK 4/6 inhibitor
7. Prior treatment with a PD-1 or PD-L1 inhibitor
8. Those who have not recovered from adverse events \leq Grade 1 from prior therapy, with the exceptions of alopecia of any grade or stable peripheral neuropathy \leq Grade 2
9. Subjects may not receive concomitant anticancer agents or radiation. Antiviral agents aimed at treating infectious hepatitis are permitted
10. History of or suspected hypersensitivity to nivolumab or abemaciclib
11. Uncontrolled ascites
12. Esophageal varices requiring treatment within the past 6 months (banding or medication)
13. Subjects with uncontrolled brain metastases. Subjects with brain metastases must have stable neurological status following local therapy (surgery or radiation) for at least 4 weeks prior to first study treatment and must be off of steroids related to the brain metastases.
14. Any concurrent condition requiring the continued or anticipated use of systemic steroids beyond physiologic replacement dosing (excluding non-systemic inhaled, topical skin, nasal, and/or ophthalmic corticosteroids). All other systemic corticosteroids above physiologic replacement dosing must be discontinued at least 4 weeks prior to first study treatment
15. Active drug or alcohol use or dependence as documented in the chart that, in the opinion of the investigator, would interfere with adherence to study requirements
16. Active bacterial or fungal infection requiring IV therapy at the start of protocol treatment
17. A second primary malignancy that, in the judgment of the investigator, may affect the interpretation of results
18. Any illness or condition that in the opinion of the investigator may affect the safety of the subject or the evaluation of any study endpoint (e.g. interstitial lung disease, severe dyspnea at rest or requiring oxygen therapy, history of major surgical resection involving the stomach or small bowel, or preexisting Crohn's disease or ulcerative colitis or a preexisting chronic condition resulting in baseline Grade 2 or higher diarrhea)
19. Personal history of ventricular tachycardia, ventricular fibrillation, or sudden cardiac arrest
20. Prior organ allograft or allogeneic bone marrow transplantation
21. Pre-existing thyroid abnormality with thyroid function that cannot be maintained in the normal range with medication

CONFIDENTIAL

This material is the property of the University of Pennsylvania.

22. Active autoimmune disease, except for vitiligo, type 1 diabetes mellitus, asthma, atopic dermatitis, or endocrinopathies manageable by hormone replacement; other autoimmune conditions may be allowable at the discretion of the Principal Investigator
23. Any other conditions judged by the investigator that would limit the evaluation of the subject
24. HIV positive by PCR

4.3 Subject Recruitment

Subjects will be identified through the clinical practices of the Abramson Cancer Center and the Hospital of the University of Pennsylvania and its affiliated hospitals and through referrals from outside hospitals and physicians. The trial will be publicized on the websites of the Abramson Cancer Center and the Hospital of the University of Pennsylvania. This protocol will also be listed in the ClinicalTrials.gov database. Subjects will be required to give written consent to participate before any screening tests or evaluations are conducted.

4.4 Total Number of Subjects and Sites

Twenty-seven evaluable subjects will be enrolled. Subjects may be enrolled at the University of Pennsylvania or at the Penn Presbyterian Medical Center.

4.5 Vulnerable Populations

Children, pregnant women, fetuses, neonates, or prisoners are not included in this research study

Note: Subjects who become imprisoned or are court-ordered to attend residential alcohol and other drug treatment facilities will be considered prisoners under Subpart C of the federal regulations 45CFR46. Such subjects cannot be continued in the research unless an amendment to the protocol is submitted and approved by the IRB and certification is submitted to the federal Office of Human Research Protections if the research is supported by the Department of Health and Human Services.

5 Study Intervention

5.1 Description

Abemaciclib is an oral tablet that is available in four dosage forms and strengths:

-50 mg tablets: oval beige table with "Lilly" debossed on one side and "50" on the other side

5.2 Intervention Regimen

Abemaciclib will be taken by mouth twice daily

5.3 Receipt

Abemaciclib will be receive to the Investigational Drug Service (IDS) and will be stored at room temperature as per standard pharmacy practice

5.4 Storage

Store at 20°C to 25°C (68°F to 77°F); excursions permitted to 15°C to 30°C (59°F to 86°F)

5.5 Preparation and Packaging

Abemaciclib is supplied for clinical use in bottles containing 60 tablets (tablets described in section 5.1).

5.6 Administration and Accountability

Upon completion of study participation or termination of the study, all unused and/or partially-used abemaciclib will be destroyed by IDS.

CONFIDENTIAL

This material is the property of the University of Pennsylvania.

